# 6.1.1 Statistical Analysis

All summary tables and data listings will be prepared by QST Consultations, Ltd., utilizing SAS® Version 9.3 or later software.

The standard operating procedures of QST Consultations, Ltd. will be followed in the creation and quality control of all data displays.

#### **6.1.2** Baseline Definition

No change from baseline summaries will be created.

# 6.1.3 Visit Windowing

Data will be provided in by-subject listings based on nominal visit indications.

# 6.1.4 Adjustments for Covariates

No inferential statistical analyses are planned.

### 6.1.5 Handling of Dropouts or Missing Data

Summary statistics will generally be reported based upon observed data. Should a determination of treatment period (on treatment, pre-treatment, post-treatment) be required for AEs or concomitant medication but the corresponding date is missing, or is a partial date, the event/medication will be considered on treatment unless the portions of the date that are available indicate this is not possible.

#### **6.1.6** Multicenter Studies

The clinical study will be conducted under a common protocol for each investigational site with the intention of pooling all the data for summaries. Every effort will be made to promote consistency in study execution at each study site.

# 6.1.7 Multiple Comparisons/Multiplicity

No inferential statistical analyses are planned.

# **6.1.8** Examination of Subgroups

No subgroup summaries will be created.

# 6.2 Disposition of Subjects

An accounting of all enrolled subjects by disposition will be presented. Subjects who discontinue study drug prematurely or withdraw from the study will be summarized and listed, with a description of the reason for early termination/withdrawal.

The number of subjects included in the safety population will be summarized. Subjects who are excluded from the safety population will be summarized by the reasons for exclusion.

#### **6.3** Protocol Deviations

Protocol deviations will be presented in a data listing.

# 6.4 Data Sets Analyzed

# 6.4.1 Safety Population

All subjects who receive at least 1 confirmed dose of study drug and have at least 1 post-baseline safety assessment or a reported TEAE will be included in the safety population. All analyses will be performed using the safety population.

# 6.5 Demographic and Other Baseline Characteristics

Sex, race, and ethnicity will be summarized by counts and percentages. Age, height (cm), and weight (kg) will be summarized with descriptive statistics.

Medical histories will be coded using MedDRA and presented in a by-subject listing.

Disease history (PN, AD, psoriasis) will be presented in a by-subject listing.

#### 6.6 Prior and Concomitant Medications

Prior and concomitant medications will be coded by the WHO-DD to Anatomical Therapeutic Classification (ATC) and preferred drug name.

A by-subject listing of all prior and concomitant medications will be presented. The associated by-subject listing will have a prior/concomitant determination that is based on the date of first dose.

# 6.7 Analysis of Efficacy

Efficacy data will be provided in by-subject listings.

# **6.8** Safety Evaluation

# **6.8.1** Extent of Exposure

The extent of exposure to study drug will be summarized by days with exposure and total number of tablets used. Subjects will be considered having 6-Month exposure if the date of first dose – date of last dose + 1 is greater than or equal to 182 days. Subjects will be considered having 1-Year exposure if date of first dose – date of last dose + 1 is greater than or equal to 358 days, considering the allowable -7 day window for the Week 52 visit.

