5.3 Dosing Regimen

During the treatment period, subjects will take one seriopitant 5 mg tablet once daily orally. Subjects will be instructed to take all doses from Baseline Visit (Study Day 1) until the Week 52 Visit, once a day. Study drug may be taken with or without food.

Should the study drug be withheld (without intent to discontinue study drug, Section 5.6), the drug may be resumed at the discretion of the investigator, at the same dosing regimen.

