5.9 Treatment Compliance

Records of study drug used, dosages administered, and intervals between visits will be kept during the study. Subjects will be asked to return all partially used and empty bottles to the study site at each visit. The site staff will count and record the number of remaining tablets in each returned bottle. Missed doses will be recorded as reported by the subject. A subject who has deviated significantly from the once-daily dosing regimen will be counseled.

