6.4.9 Week 52 Visit

The Week 52 Visit occurs 364 days (\pm 7 days) after the Baseline Visit. At the Week 52 Visit, the following procedures and assessments are to be performed:

- Register visit into the IWRS
- Review menstrual diary and record dates of menstrual flow (if applicable)
- Assess and record any AEs and/or SAEs
- Assess and record any changes in the subject's concomitant medications
- Female subjects should be queried for presence of new breast masses or abnormal discharge, and abnormal vaginal bleeding or discharge
- Perform targeted physical examination, including weight
- Obtain ECG
- Obtain vital signs
- Draw blood for clinical laboratory tests
 - Hematology

- Chemistry
- Endocrine
- Reproductive endocrine labs for females under 55 years of age at consent
- Perform a urine pregnancy test for females of childbearing potential (with positive or equivocal results to be confirmed by a serum pregnancy test)
- Ask subject to complete WI-NRS
- Ask the subject to complete the following questionnaires:
 - DLQI
 - HADS
 - ESS
- Perform IGA PN-S (for subjects with PN only)
- Obtain photos (only PN subjects that signed photography consent, only at sites selected for photography)
- Collect returned study drug
- Confirm next scheduled visit date

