Table 14.1.1.1: Summary of Subject Demographics (Safety Population)
(Page 1 of 2)

	Serlopitant 5 mg
	(N=xxx)
Age (years)	
n	XXX
Mean	XX.X
SD	XX.XX
Median	XX.X
Min. to Max.	xx to xx
Sex	
n	XXX
Male	xx ( xx.x%)
Female	xx ( xx.x%)
Ethnicity	
n	XXX
Hispanic or Latino	xx ( xx.x%)
Not Hispanic or Latino	xx ( xx.x%)
Race	
n	XXX
American Indian or Alaska Native	xx ( xx.x%)
Asian	$\mathbf{x}\mathbf{x}  (\mathbf{x}\mathbf{x}.\mathbf{x}\%)$
Black or African American	XX (XX.X%)
Native Hawaiian or Other Pacific Islander	XX (XX.X%)
White	XX (XX,X'')
Multiple/Other	$\mathbf{x}\mathbf{x}  (\mathbf{x}\mathbf{x}.\mathbf{x}\%)$
Transpio Onio	AA ( AA.A./0)

Table 14.1.1.1: Summary of Subject Demographics (Safety Population)
(Page 2 of 2)

	Serlopitant 5 mg (N=xxx)
Height (cm)	(IV AAA)
N	XXX
Mean	XX.X
SD	XX.XX
Median	XX.X
Min. to Max.	xx to xx
Weight (kg)	
n	XXX
Mean	XX.X
SD	XX.XX
Median	XX.X
Min. to Max.	xx to xx

Table 14.3.0.1: Summary of Extent of Exposure (Safety Population)

	Serlopitant 5 mg (N=xxx)
otal Number of Tablets Used	XXX
n	XXX
Mean	XX.X
SD	XX.XX
Median	XX.X
Min. to Max.	xx to xx
otal Number of Days of Exposure	XXX
n	XXX
Mean	XX.X
SD	XX.XX
Median	XX.X
Min. to Max.	xx to xx
Subjects with 6-Month Exposure a	xx ( xx.x%)
Subjects with 1-Year Exposure a	xx ( xx.x%)

<sup>a Subjects considered having 6-Month exposure if date of first dose – date of last dose + 1 is greater than or equal to 182 days.

Subjects considered having 1-Year exposure if date of first dose – date of last dose + 1 is greater than or equal to 358 days, considering the allowable -7 day window for the Week 52 visit.

Table 14.3.1.1.1: Overall Summary of Treatment-Emergent Adverse Events (TEAEs) (Safety Population)

	Serlopitant 5 mg
	(N=xxx)
Subjects with any TEAE	XX ( XX.X%)
Number of TEAEs	XXX
Subjects with any Related TEAE	xx ( xx.x%)
Number of Related TEAEs	XXX
Subjects with any Serious TEAE	xx ( xx.x%)
Number of Serious TEAEs	XXX
Subjects with any Related Serious TEAE	xx ( xx.x%)
Number of Related Serious TEAEs	XXX
Subjects who Died	xx ( xx.x%)
Subjects who Discontinued Study Drug Due to TEAE	xx ( xx.x%)
Maximum Severity by Subject	
Grade 5	$XX \left( XX.X^{0}/_{0} \right)$
Grade 4	xx (xx.x%)
Grade 3	xx ( xx.x%)
Grade 2	xx ( xx.x%)
Grade 1	xx ( xx.x%)
Maximum Relationship by Subject	
Likely Related	xx ( xx.x%)
Likely Unrelated	xx ( xx.x%)

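### The 6-month and 1-year exposure counts measure the calendar span from first to last dose, so subjects with long permitted interruptions count as fully exposed

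*SAP*

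**What the plan says.** SAP 6.8.1 begins: "The extent of exposure to study drug will be summarized by days with exposure and total number of tablets used". It does not say whether days with exposure means the whole interval between first and last dose or only the days on which drug was taken.

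The next two sentences define the categories. A subject has 6-month exposure "if the date of first dose – date of last dose + 1 is greater than or equal to 182 days", and 1-year exposure "if date of first dose – date of last dose + 1 is greater than or equal to 358 days". The second cut-off is explained as "considering the allowable -7 day window for the Week 52 visit". Footnote a of Table 14.3.0.1 repeats both rules, and the table shell carries a row for each category (for example "Subjects with 1-Year Exposure").

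Protocol 5.3 (Version 3.0) covers drug withheld without intent to discontinue: "the drug may be resumed at the discretion of the investigator, at the same dosing regimen". It gives no maximum length or number of interruptions. Protocol 5.9 provides for counts of returned tablets and adds: "Missed doses will be recorded as reported by the subject". Protocol 8.6 plans a compliance calculation from tablet counts, but none of the tables indexed in SAP Section 9 reports compliance.

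**The concern.** The category rules look only at the two end dates. A subject who stops for two months and resumes is indistinguishable from one who took a tablet every day. The introductory sentence of 6.8.1 names two measures that could separate them, days with exposure and tablets used, but neither feeds the categories.

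Long-term safety is the primary objective. After early termination the SAP was cut back for an abbreviated report, and the two category rows are the only planned counts of subjects who reached a long-term exposure mark. A reader of the report will take them as the number of people treated for six months or a year. If some of that time was off drug, the counts overstate the dosing behind the safety conclusion.

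**Working it through.** **Inputs**
- Cut-offs of 182 and 358 days: SAP 6.8.1 and Table 14.3.0.1 footnote a.
- Week 52 timing: "The Week 52 Visit occurs 364 days" after Baseline, with a window of 7 days either side (Protocol 6.4.9).
- One tablet once daily from Day 1 until the Week 52 visit (Protocol 5.3).
- Plasma half-life of 45-86 hours (Protocol 1.2.1).
- Lengths of withheld periods: assumed and shown as a range, because the documents give none.

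**Step 1: reproduce the SAP's own figures.** The earliest allowed Week 52 visit is 364 − 7 = 357 days after Baseline. The inclusive span is 357 + 1 = 358, which matches the 1-year cut-off. The 6-month cut-off is 26 × 7 = 182. Both are calendar spans.

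**Step 2: read the rule in its workable direction.** The SAP writes first dose minus last dose plus 1. Taken literally, dose dates 357 days apart give −357 + 1 = −356, and dose dates 181 days apart give −180, so nobody would qualify. The intended rule must be last minus first plus 1. This is a separate wording error; everything below assumes the intended order.

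**Step 3: compare span with dosed days.** Dosed days = span − days withheld.

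| Span (days) | Withheld (assumed) | Dosed days | Share of span | Highest category under the SAP | Highest cut-off reached on dosed days |
|---|---|---|---|---|---|
| 358 | 28 | 330 | 92.2% | 1-year | 182 |
| 364 | 56 | 308 | 84.6% | 1-year | 182 |
| 358 | 84 | 274 | 76.5% | 1-year | 182 |
| 358 | 177 | 181 | 50.6% | 1-year | neither |
| 190 | 60 | 130 | 68.4% | 6-month | neither |
| 182 | 56 | 126 | 69.2% | 6-month | neither |

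The arithmetic limit is a subject with only a first and a last tablet 357 days apart: 358 − 356 = 2 dosed days, still counted as 1-year.

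**Step 4: how long a gap matters against the 1-year mark.** Dosed days fall below 358 once the gap reaches span − 358 + 1 days. With the last dose on the day of the Week 52 visit, the inclusive span is 358 at the earliest visit, 365 at the nominal visit and 372 at the latest. The gap needed is therefore 1, 8 and 15 days respectively. No single gap length marks a subject as over-counted.

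**Step 5: is a long gap really time off drug?** Five half-lives are 5 × 45 / 24 = 9.4 days to 5 × 86 / 24 = 17.9 days. Interruptions well beyond that include time with essentially no parent drug.

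**Step 6: is it visible elsewhere in the plan?** Table 14.3.0.1 also summarises tablets used and days of exposure, and Listing 16.2.5.2 gives tablets dispensed, returned and used by bottle. The table gives these only for the whole safety population, so it does not show how many tablets the subjects in the 1-year row took.

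**The case against.** The strongest defence is that the rule is explicit, footnoted and deliberately a calendar convention. The 358-day cut-off is built to absorb the visit window. Applied directly to dosed days, it would strip 1-year status from a subject seen at the earliest allowed visit who missed one day. Short gaps also mean little pharmacologically: 7 days (168 hours) is about 2.0 to 3.7 half-lives, leaving roughly 8-26% of parent drug. This stands as a reason not to replace the span rule outright. It does not answer the case of gaps lasting weeks or months.

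A second defence is that tablets used, in the same table and the bottle listing, approximates dosed days under a once-daily regimen. This is partly right, and it makes the fix cheap. But the summary is not split by category, so the two counts remain unqualified.

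Third, the Protocol has some restraint. Section 5.6 includes persistent non-adherence to study procedures among grounds for discontinuation, and Section 5.9 calls for counselling after significant deviation from daily dosing. A reader might infer that interruptions are allowed without limit. The accurate statement is that no limit is stated.

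A reader might also infer that off-drug time dilutes the adverse-event rates attributed to long-term dosing. The SAP does not support that. TEAEs are tabulated for the entire study (6.8.2), every adverse-event shell uses one column with the safety-population N, and 6.1.8 rules out subgroup summaries. The exposure categories are not a denominator for any planned table.

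Nor can it be said that the Protocol 8.6 compliance calculation would have revealed the gaps. It does not say how withheld days enter the expected tablet count.

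**Conclusion.** The point holds for the two category counts. Under the intended last-minus-first rule, subjects with long interruptions are counted as having full 6-month or 1-year exposure, and the table does not let a reader see how much dosing lies behind those counts. The direction is certain: dosed days can equal the span but cannot exceed it, so the counts can overstate dosing and cannot understate it.

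The size is unknown. It is tempting to assume an interruption rate and a number of subjects reaching one year and then quote an over-count. The documents give neither figure, the study was terminated early, and the gap length that matters varies with the visit date (Step 4). The worked cases show what the rule permits, not how often it happened.

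The conclusion rests on two assumptions: that the subtraction is meant as last minus first, and that withheld periods of some length occurred. It is a reporting weakness with an inexpensive remedy and calls for no change to the clinical rule on withholding.

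**What to change.** In SAP 6.8.1 and Table 14.3.0.1:

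1. Keep the two span-based rows, label them as first-to-last-dose duration, and correct the order of the subtraction.
2. State whether days with exposure, and the matching table row, are the span or are net of interruptions.
3. Within each category, add a summary of total tablets used and the number of subjects whose tablets used also reach 182 (6-month) or 358 (1-year). One tablet a day makes tablets used a reasonable proxy for dosed days. State how unreturned bottles are handled, since they affect the count.
4. If start and stop dates of withheld periods were recorded, also show the categories net of those periods. The documents describe subject-reported missed doses and tablet counts but no dated withheld periods, so this step depends on what the database holds.

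The cost is a few extra table rows from the per-subject tablet totals already planned for the same table, plus a short wording change. The exposure counts may look less favourable. Because the tablet rows sit beside the span rows, a subject with one missed dose loses nothing from the span-based count.

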#### Listing 16.2.1.1: Subject Disposition Information (Page xx of yy)

S: Subject A: Age/Sex E: Evaluable	F: Date of First Dose L: Date of Last Dose	R: Reason for Treatment Discontinuation P: Primary AE Number/Specify	E: Follow-up Discontinuation Date (Day)  R: Reason for Follow-up Discontinuation	D: Date of Last Contact P: Primary AE Number/Specify
S: xxxxx A: xxxx E: xxxxxxxx	F: xxxx-xx-xx L: xxxx-xx-xx	R: xxxxxxxxx xx xxxxxxxxxxxxxxxxxxxxxxx	E: xxxx-xx-xx (xx) R: xxxxxxxxxx xx xxxxxxxxx	D: xxxx-xx-xx P: xxxxxxxxxx
S: xxxxxx A: xxxx E: xxxxxxxx	F: xxxx-xx-xx L: xxxx-xx-xx	R: xxxxxxxxx xx xxxxxxxxxxxxxxxxxxxxxxx	E: xxxx-xx-xx (xx) R: xxxxxxxxx xx xxxxxxxxx	D: xxxx-xx-xx P: xxxxxxxxxxx
S: xxxxxx A: xxxx E: xxxxxxxx	F: xxxx-xx-xx L: xxxx-xx-xx	R: xxxxxxxxx xxxx xxxxxxx xxxxx P: xxxxxxxxxx	E: xxxx-xx-xx (xx) R: xxxx xx xxxxxxxx	D: P: xxxxxxxxxx

SOURCE: USERNAME\SPONSOR\PROJECT\JOBNAME (DATE, TIME)

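### The SAP's 6-month and 1-year exposure rules subtract the dose dates in the wrong order, so as written no subject can qualify for either row of Table 14.3.0.1

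*SAP*

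**What the plan says.** SAP Section 6.8.1 plans two continuous exposure summaries: "The extent of exposure to study drug will be summarized by days with exposure and total number of tablets used". It then adds two categories. A subject has 6-month exposure if "date of first dose – date of last dose + 1 is greater than or equal to 182 days". The longer category is worded the same way, "1-Year exposure if date of first dose – date of last dose + 1", with a threshold of 358 days that the SAP explains by the 7-day early allowance on the Week 52 visit.

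Footnote a of Table 14.3.0.1, the exposure table shell in SAP Section 9, repeats both rules in the same order: "Subjects considered having 6-Month exposure if date of first dose – date of last dose + 1 is greater than or equal to 182" and "Subjects considered having 1-Year exposure if date of first dose – date of last dose + 1 is greater than or equal to 358". Neither document gives the opposite order for exposure anywhere.

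**The concern.** The subtraction runs backwards: the earlier date comes first, so every subject dosed on more than one day gets zero or a negative number. Both categories require a large positive number.

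The trial's primary objective is long-term safety, and these two rows are the only planned counts of subjects reaching 6 months and 1 year on drug. SAP Section 2 says the study was terminated early, so the number reaching each duration cannot be inferred from the design. SAP Section 6.8.2 tabulates adverse events over the entire study, whereas Protocol Section 8.8.1 had planned them by time period as well. The exposure rows therefore help show how much long-duration experience lies behind the adverse event figures.

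Two things can happen. If the rule is programmed as written, the report shows no subject with 6 months of exposure, beside a days-of-exposure summary that may plainly disagree. If the programmer corrects it without changing the text, the counts are right but the definition printed beneath them is wrong, and anyone reproducing the table from the SAP gets zero.

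**Working it through.** **Inputs**

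- Thresholds of 182 and 358 days: SAP Section 6.8.1 and Table 14.3.0.1, footnote a.
- Week 52 timing: Protocol Section 6.4.9, "The Week 52 Visit occurs 364 days" after Baseline, with a window of ±7 days.
- Dosing runs from Baseline, which is Study Day 1, to the Week 52 visit: Protocol Section 5.3. The last dose therefore cannot precede the first.
- The SAP's own day count: the listing footnotes (for example Listing 16.2.1.1) take the event date, subtract the first dose date and add 1, for dates on or after first dose.

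**Step 1: reproduce the plan's 358.** The earliest in-window Week 52 visit is 364 − 7 = 357 days after Baseline. Counting both end days gives 357 + 1 = 358, the SAP's figure. This is last dose minus first dose plus 1. Likewise 182 = 26 × 7, so the 6-month threshold is 26 weeks.

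**Step 2: evaluate the printed formula.** Let d be the number of days from first to last dose, with d ≥ 0.

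- As printed: first − last + 1 = 1 − d. The maximum is 1, at d = 0.
- Reversed: last − first + 1 = d + 1, which is the study day of the last dose.

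| d (days) | Study day of last dose | As printed | Reversed |
|---|---|---|---|
| 0 | 1 | 1 | 1 |
| 181 | 182 | −180 | 182 |
| 357 | 358 | −356 | 358 |
| 364 | 365 | −363 | 365 |
| 371 | 372 | −370 | 372 |

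**Step 3: compare with the thresholds.** Of the 372 values of d from 0 to 371, none reaches 182 or 358 as printed. With the dates reversed, 182 is first met at d = 181 and 358 at d = 357.

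**Step 4: what else uses the formula.** The row for "Number of Days of Exposure" in the same table has no printed formula, and tablets used is a separate tablet summary. Neither is defined by the reversed expression.

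**The case against.** The strongest reply is that this is a transposition with only one sensible reading. The 358-day derivation and the listing footnotes both point to last minus first plus 1, so the wording gives the analyst no real choice. A literal program would print zeros directly beneath the days-of-exposure statistics, and SAP Section 6.1.1 puts all displays under the vendor's quality control, so the error would probably be caught. Table 14.0.1.1 counts subjects who completed treatment, which is close to a 1-year count. The disposition listings print both dates for each subject ("F: Date of First Dose L: Date of Last Dose"), so the rows can be rebuilt. No population, denominator or test depends on them.

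Much of this stands. The intent is recoverable, silent correction is the likelier outcome, and the four occurrences are one error repeated. The dash could loosely be read as meaning from first dose to last dose, but the added 1 marks a subtraction.

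The reply does not remove the point. Treatment completion is neither a 6-month count nor the 358-day rule. Being able to rebuild the rows from listings does not correct a definition printed in the report. Relying on a programmer to depart from the written rule leaves the SAP and the output in disagreement. It is also fair to note that the SAP does not say how total days of exposure is computed; all that can be said is that the reversed formula does not define it.

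**Conclusion.** The concern holds. As written, both categorical rows of Table 14.3.0.1 are 0 for any data set: the largest attainable value is 1, against thresholds of 182 and 358. The planned enrolment is up to 700; the documents do not give the number enrolled, and the result does not depend on it. Under the intended order, a subject whose last dose falls on an in-window Week 52 visit scores 358 to 372 instead of −356 to −370. That range assumes the last dose is taken on the day of the visit.

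The more likely practical result is correct counts under an incorrect footnote. The safety population and adverse event incidence are unaffected. Because the rule is an operative definition that also prints in the table, it should be corrected before the table is produced.

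**What to change.** In SAP Section 6.8.1 and in footnote a of Table 14.3.0.1, restate both rules as last dose date minus first dose date plus 1, keeping the thresholds of 182 and 358 days. That is four occurrences in two places. Then check that the program for Table 14.3.0.1 subtracts in the same order. The cost is a wording correction and one program check; no new data are needed.
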